### **Study design.**

- On the day of admission to the pediatric surgery service of the hospital, the potential participant and parents of the study in progress will be informed. First, patients and parents will be informed about the possibility of voluntary participation in the study. Next, the objective, process and potential benefits of this will be reported. The consent of the legal guardians will then be requested. They will be asked to fill in the information of the demographic and clinical variables, answering the self-assessment instruments (the data collection will have an estimated time of 30 'per subject), both children and parents / companions. After the surgical intervention and within a period comprised in the first 5 days, an evaluation of the dependent variables (intensity, location and distribution of pain) will be carried out in both children and parents. They should fill in the self-assessment instruments in the same way as in the pre-surgery session (this will take approximately 10 minutes).
- At 10 days, 3 months, 6 months and 12 months after the intervention, will contact the patients and relatives by telephone, and they will be asked to reply again to the evaluation of all the variables. The evaluation will be carried out by telephone interview.
- The information sheet, the informed consent, and the evaluation instruments will be collected by a researcher, stored and guarded in the Department of Radiology, Rehabilitation and Physiotherapy of the Complutense University of Madrid. Thus, complying with the provisions of Organic Law 3/2018, of December 5, on the Protection of Personal Data and guarantee of digital rights.

## **Ethical Aspects**

The study has the approval of the research commission of the Faculty of Nursing, Physiotherapy and Podiatry of the Complutense University of Madrid. Also, with the favorable opinion of the research commission of the Hospital 12 de Octubre Research Institute (i + 12). Lastly, it will be evaluated by the Ethics Committee of the research institute Hospital Universitario 12 de Octubre de Madrid (1 + 12).

The study will comply with all the ethical principles of the Declaration of Helsinki. All participants will participate in the study on a voluntary basis. They will be informed of the objective of the study, the procedure, and the process of carrying it out. In addition, the informed consent of each participant and their guardians will be required, which may be revoked at any time. In addition, they are within their right to know the results of the investigation once it has been completed.

The clinical and personal information will be totally confidential where the researchers will comply with the confidentiality commitments of the hospital center and the Faculty of Nursing, Physiotherapy and Podiatry. The treatment, communication and transfer of personal data of all participating subjects will comply with the provisions of the General Regulations for the Protection of Personal Data (Regulation 2016/679 of the European Parliament) and Organic Law 3 / 2018, of December 5, Protection of Personal Data and guarantee of digital rights.

The study does not hinder, modify, or interfere with routine clinical practice. Nor does it modify the service care protocols. The time of data collection is estimated at 30'. This time is not excessive for patients and their families and can provide

Chronic postsurgical pediatric pain. Observational Study. [name] et al. 15 December 2020. University Complutense of Madrid.

very relevant research and clinical information in order to understand the mechanisms of chronic pain in the pediatric population. This could save on medical care after the intervention, shortening the periods of hospitalization and readmission.

Therefore, it is considered that carrying out the study complies with the ethical and research standards and that the benefits in knowledge in the field that can be derived from it could significantly improve the healthcare activity, not assuming the realization of this, a serious damage to patients, families or professionals.

CHRONIC POSTSURGICAL PEDIATRIC PAIN.

TITLE: RISK FACTORS TO DEVELOP CHRONIC POSTSURGICAL PEDIATRIC PAIN

INVESTIGATOR PRINCIPAL: [name]

PROJECT ENTITIES: COMPLUTENSE UNIVERSITY OF MADRID & 12 OCTUBRE PEDIATRIC HOSPITAL.

NUMBER OF IDENTIFICATION: 26/618

DATE: 15TH December 2020.

Statistical Analysis Plan

The results will be analyzed with the SPSS 25 statistical program (SPSS, Inc., Chicago, IL, USA). The interpretation of the statistical tests will be carried out based on a significance level of 5% ($P < 0.05$). First, the demographic variables of the sample will be presented as mean \pm standard deviation (SD), in the case of quantitative variables, and as an absolute value (relative frequency percentage in the case of qualitative variables).

The correlation of the risk factors of both children and parents with chronic postsurgical pain in children will be analyzed. To do this, the Pearson Correlation Coefficient will be used, categorizing the magnitude of the correlation as follows: strong (> 0.60), moderate (0.30-0.60), and weak or very weak (< 0.30).

Additionally, a multiple linear regression model will be used to determine the degree of association between risk factors and chronic postsurgical pain. Specifically, the intensity and location of pain will be included as criterion variables, while catastrophizing, anxiety, fear of pain, fear of movement and quality of life will be considered as predictor variables. The degree of multicollinearity existing between the predictor variables will be evaluated using the Variance Inflation Factor (VIF). The strength of association will be examined using the adjusted coefficient of determination (adjusted R^2). In addition, the regression coefficient (B), the P -value and the standardized beta coefficient (β) will be calculated for each predictor variable of the reduced final model. Thus, it will be possible to determine the variables that most directly influence the regression model.

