## STUDY PROTOCOL

**Type of Study:** Observational longitudinal prospective. The study has approved by etic comity of clinical research of Hospital 12 de octubre de madrid.

**Target population:** Pediatric population undergoing surgery intervention in 12 de octubre hospital.

**Sample:** A convenience sampling will be carried out among the patients undergoing surgical intervention according eligibility criteria.

- **Inclusion criteria:** Children with age from 4 years to 18 years. Undergoing surgery for any surgical specialty. ASA Status (American Society of Anesthesiologist) from I to III.
- **Exclusion Criteria:** Children who do not understand and speak Spanish correctly. Children with verbal communication problems.
- **Stratification of the sample:** The sample will be divided into 2 sample groups: a) children into 4 to 8 years, and b) children into 8 to 18 years.
- **Sample size:** To assess the degree of association between the different clinical variables and the development of chronic postsurgical pain in the pediatric population, the calculation of the sample size was based on previous literature that proposes 20 cases per variable in order to estimate a prediction model in a relatively stable manner. Therefore, taking into account that a total of 13 predictor variables were used (anxiety, catastrophism, fear of pain, fear of movement, pain interference, disability, limitation of activities, prediction of chronic pain in children and

catastrophism, anxiety, fear of pain, fear of movement of parents / guardians / companions), it was considered necessary to include at least 260 children undergoing surgery to meet the objective of this study

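### Pearson's r and linear regression do not suit pain location, and the fixed strength bands can understate a risk factor if chronic pain is yes/no or intensity has many zeros

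*SAP*

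**What the plan says.** The correlation paragraph of the SAP sets the aim: "The correlation of the risk factors of both children and parents with chronic postsurgical pain in children will be analyzed". It names one coefficient and grades it by fixed bands: "the Pearson Correlation Coefficient will be used, categorizing the magnitude of the correlation as follows: strong (> 0.60", with 0.30 to 0.60 as moderate and anything below 0.30 as weak or very weak. No rank-based, nominal or binary method is mentioned.

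The regression paragraph of the SAP then specifies a multiple linear model in which "the intensity and location of pain will be included as criterion variables". Strength of association is read there from adjusted R², with B, P and standardized beta for each predictor that stays in the model.

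In the protocol, the Study design section calls for an "evaluation of the dependent variables (intensity, location and distribution of pain" after surgery, with further telephone assessments at 10 days and at 3, 6 and 12 months. The sample size paragraph describes the target as "the development of chronic postsurgical pain in the pediatric population". Neither document gives a scale for intensity, a coding for location, a case definition for chronic pain, an expected incidence, or the call at which the correlation or the regression is to be run.

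**The concern.** Pearson's r and linear regression both treat the outcome as a number whose order and spacing carry meaning. Pain site has neither. Codes for body sites are labels, and any coefficient computed on them describes the labelling as much as the children.

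The second difficulty is the fixed grading. The sample is an unselected surgical population, any specialty, followed to 12 months, so it is plausible that many children will report no pain at the later calls. If the outcome is then a yes/no classification, or an intensity score with a large block of zeros, the size of r reflects how common pain is as well as how closely the risk factor tracks it. A cut-off of 0.60 then means something different at each pain frequency. What is at stake is the ranking of child and parent risk factors: a factor could be set aside as moderate or weak because pain was uncommon at the call analysed.

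**Working it through.** **The plan's own figures.** The bands are stated without derivation, so there is nothing to reproduce for them. The sample size follows as 20 × 13 = 260; it is used below only as n for sampling error.

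**Location.** Suppose K sites are coded 1 to K. Replacing each code k by K + 1 − k describes the same children and turns r into −r. Swapping two codes in general changes the size of r too. The same holds for B, beta and adjusted R² in a linear model. No assumption about pain frequency is needed, and no direction of bias can be stated.

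**Chronic pain as yes/no (assumed form).** Take a normal predictor and a yes/no outcome cut from a latent normal variable at prevalence p. Then

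r observed = ρ × φ(z_p) / √(p(1 − p)),

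where ρ is the latent correlation, z_p the normal quantile at p and φ the normal density. All prevalences are assumptions.

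| Assumed p | Multiplier (largest possible r) | ρ = 0.70 reads | ρ = 0.80 reads | ρ needed to reach 0.60 |
|---|---|---|---|---|
| 5% | 0.473 | 0.33 | 0.38 | not attainable |
| 10% | 0.585 | 0.41 | 0.47 | not attainable |
| 20% | 0.700 | 0.49 | 0.56 | 0.86 |
| 30% | 0.759 | 0.53 | 0.61 | 0.79 |
| 50% | 0.798 | 0.56 | 0.64 | 0.75 |

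The last column is 0.60 divided by the multiplier; at 5% and 10% that exceeds 1. A latent 0.61 at 5% reads 0.61 × 0.473 = 0.29, which is in the weak band.

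**Intensity as a 0–10 score (assumed form).** This was simulated with 1,000,000 bivariate normal draws (Spearman on 200,000 of them), with y the latent outcome.

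- Roughly symmetric score, 5 + 2y rounded and limited to 0–10: latent 0.61, 0.70 and 0.80 give Pearson 0.603, 0.692 and 0.791. The loss is about 0.01 and no band changes.
- Zero-heavy score, zero below a cut-off c and 4(y − c) rounded up and limited to 1–10 above it, latent 0.70:

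| Assumed share of zeros | Pearson | Spearman |
|---|---|---|
| 50% | 0.61 | 0.63 |
| 70% | 0.54 | 0.55 |
| 80% | 0.48 | 0.49 |
| 90% | 0.39 | 0.39 |

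Ranks recover almost nothing, because the tied zeros cause the loss. The bands do not transfer to Spearman in any case: in the symmetric setting a latent 0.61 gives a Spearman coefficient of 0.585, below the cut.

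**Sampling error at the cut.** By Fisher's z with n = 260, the chance that an observed r exceeds 0.60 when the true value is 0.61 is Φ[(atanh 0.61 − atanh 0.60) × √257] = 0.60. An observed r of 0.61 has a 95% interval of 0.53 to 0.68. A label without an interval hides this.

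**The case against.** A reader might infer that the outcomes are recorded as 0–10 scores or as yes/no, and that truly strong risk factors would therefore be reported as only moderate. The documents support neither step. No scale or case definition is given, so both formats are assumptions. The shift in label is not general either: a symmetric score keeps its band, a latent 0.70 with 50% zeros still reads 0.61, and a latent 0.80 with a yes/no outcome at 30% still reads 0.61.

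The ceilings in the yes/no table also depend on a normal predictor. With an exponential predictor, taken as an illustration, the largest possible r is ln(1/p) × √(p/(1 − p)): 0.69, 0.77, 0.80 and 0.79 at 5, 10, 20 and 30%. So it would be wrong to say that below some prevalence no factor can be graded strong. The documents give no distribution for any predictor.

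It can also be said that the bands describe the observed r, so an r of 0.49 called moderate is correctly labelled by the SAP's own definition. That stands: *understate* here means relative to a latent correlation, which the SAP does not name as its target. The SAP also does not plan to compare labels between calls or age groups, so non-comparability is a caution about use, not a fault in a planned analysis.

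Finally, the regression offers a second measure of strength, and the text ties location explicitly to the regression, not to Pearson's r. Both remarks are fair, but neither removes the problem. Linear regression on site codes fails for the same reason as Pearson's r. Adjusted R² for a zero-heavy intensity is reduced as well: with one predictor R² is r², so 0.70² = 0.49 becomes 0.48² = 0.23 at 80% zeros.

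**Conclusion.** The point holds in two parts of different strength.

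For location it is firm and needs no numerical assumption. The SAP makes a nominal variable the outcome of a linear model and offers no method that suits it. If site codes also enter the correlation, which the text leaves open, the same fault applies there.

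For development of chronic pain and for intensity it is conditional. If the outcome is yes/no or zero-heavy, fixed bands can understate a risk factor, by roughly 0.1 to 0.4 on a latent correlation of 0.70 across the ranges shown (0.70 − 0.61 = 0.09 at 50% zeros; 0.70 − 0.33 = 0.37 for yes/no at 5%). If intensity is roughly symmetric, the effect is negligible. The prevalences of 5–50%, the zero shares of 50–90%, the normal predictor and the 0–10 format are assumptions. The documents cannot settle which case applies, because the outcome, its coding and its call are undefined; that gap is the root of the matter and should be closed before analysis.

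**What to change.** 1. State which outcome, with its scale or coding, and which follow-up call enter the correlation and the regression.
2. Analyse location with a nominal method, such as comparing predictors across sites or multinomial logistic regression. Do not compute Pearson's r or fit a linear regression on site codes.
3. If development of chronic pain is analysed as yes/no, give its case definition, use logistic regression, and report the odds ratio per SD of each risk factor with a 95% confidence interval, plus the c-statistic.
4. For intensity, report the correlation coefficient with a 95% confidence interval, using Spearman if the scores are skewed. Say that Spearman alone does not cure a large block of zeros.
5. Drop the 0.30 and 0.60 bands, or mark them as descriptive only, and do not compare labels across calls or age groups.

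The cost is SAP wording and a little more analysis; the software named in the SAP can do all of it. The downside is losing a single, simple strength label for each risk factor.

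### P-values for pain intensity rest on constant error variance with no safeguard; the standard error of a real risk factor may be too small if zeros are very common or scores are right-skewed

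*SAP*

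**What the plan says.** The regression paragraph of the SAP says that "a multiple linear regression model will be used to determine the degree of association between risk factors and chronic postsurgical pain". For the outcome it adds: "Specifically, the intensity and location of pain will be included as criterion variables". On the other side of the equation, "catastrophizing, anxiety, fear of pain, fear of movement and quality of life will be considered as predictor variables". Tests are read "based on a significance level of 5" per cent, and "the regression coefficient (B), the P -value and the standardized beta coefficient (β) will be calculated for each predictor variable of the reduced final model". No confidence intervals are mentioned.

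The only diagnostic named is the variance inflation factor, which concerns correlation among predictors and says nothing about error variance. The SAP names no residual check, robust standard error, bootstrap or alternative model for intensity.

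The Protocol admits children having surgery in any specialty, does not make pain an entry criterion (Sample, inclusion criteria), and follows them by telephone at 10 days and at 3, 6 and 12 months (Study design). Neither document gives a pain scale, an expected prevalence of chronic pain or a share of zero scores. The SAP does not say which visit supplies the outcome.

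**The concern.** Least-squares P-values use one pooled residual variance for every child. An intensity score with many zeros need not behave like that. Children at low risk cluster at zero with little scatter, while children at high risk are a mixture of zeros and positive scores with much more. If the children with the most extreme questionnaire scores are also those with the most scatter, the pooled variance understates the uncertainty of B for that questionnaire.

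The study exists to identify risk factors, and the SAP uses the coefficients and P-values of this model to say which variables matter most. At stake is overstated precision for the factors that truly matter, and some false flags for factors that are only correlated with them. The point concerns the intensity model; location of pain as an outcome is a separate question.

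**Working it through.** **1. The plan's own figure.** The Protocol's sample-size paragraph uses "20 cases per variable in order to estimate a prediction model in a relatively stable manner" and says "a total of 13 predictor variables were used". 20 × 13 = 260, which reproduces the stated minimum. This n is used throughout, with no dropout assumed.

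**2. Why the variance moves.** Let π be the chance of any pain, and μ and σ the mean and SD of intensity among children in pain. Then

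Var(Y) = π(1 − π)μ² + πσ².

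Take a child one SD above average on a factor with an assumed odds ratio of 2, and look at π(1 − π):

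- π = 0.10: odds 0.111 → 0.222, π → 0.182. The term goes from 0.090 to 0.149, a ratio of 1.65.
- π = 0.20: odds 0.25 → 0.50, π → 0.333. From 0.160 to 0.222, a ratio of 1.39.
- π = 0.50: odds 1 → 2, π → 0.667. From 0.250 to 0.222, a ratio of 0.89.

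The term rises steeply when pain is rare. Near one half it falls, while πσ² still rises, so the two partly offset.

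**3. Why skew matters.** For one standardised predictor x with error variance v(x), in large samples,

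(true variance of B) / (usual variance of B) = E[x²v(x)] / E[v(x)].

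If v(x) = a + bx, this equals 1 + (b/a) × skewness of x. With a symmetric score a linear rise in variance cancels out, and only its curvature, strongest when pain is rare, does harm. With a right-skewed score the usual standard error is too small.

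**4. Simulation with five predictors.** This matches the number of constructs the SAP names. Assumed: pairwise correlation 0.4; intensity zero or 1-10 centred near 4; one real predictor with odds ratio 1.5, 2 or 3 per SD plus 0.3 to 0.5 points per SD among children in pain; two-sided 5% tests; 3000 runs per setting. Entries are the usual standard error of the real factor divided by its true sampling SD.

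| Zeros | Normal scores | Right-skewed (log-normal) scores |
|---|---|---|
| 50% | 1.01-1.06 | 0.94-0.96 |
| 60% | 1.01-1.04 | 0.90-0.92 |
| 70% | 0.97-1.01 | 0.84-0.86 |
| 80% | 0.93-1.00 | 0.75-0.78 |
| 90% | 0.83-0.95 | 0.58-0.66 |

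Monte Carlo error on the ratios is about 0.013. With HC3 the ratio was 0.98 to 1.05 in every setting.

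**5. How much depends on skew.** Two predictors, latent correlation 0.5, log-odds 0.8 per SD, at least 2000 runs per setting. A range means that separate runs differed.

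| Skewness | In pain | Usual SE / true SD | Shortfall |
|---|---|---|---|
| 0 | 20% | 0.97-1.00 | 0-3% |
| 0 | 10% | 0.89-0.92 | 8-11% |
| 1.3 | 20% | 0.88 | 12% |
| 1.75 | 20% | 0.124/0.145 = 0.86 | 14% |
| 2.9 | 20% | 0.81 | 19% |
| about 6 | 20% | 0.71-0.73 | 27-29% |
| 1.3 | 10% | 0.72 | 28% |

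A cross-check: a ratio of 0.88 makes a nominal 95% interval reach 1.96 × 0.88 = 1.72 true SDs, which covers about 92%; the simulated coverage was 92%. A ratio of 0.73 gives 1.43 and about 85%; simulated, 84%.

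**6. False positives.** If no predictor matters, the variance is constant and rejection was 4-6% at every zero share. For a null predictor correlated with a real one, rejection was about 5-9% at 20% in pain and up to about 12% at 10%. HC3 lowered this but did not always return it to 5%: it gave 4-7% with five predictors, and 6-11% at 10% in pain with two skewed predictors.

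**The case against.** A reader might infer that a mostly-zero outcome by itself makes the standard errors of real risk factors too small. The documents do not support that. They give no zero share, pain scale, score distribution or effect size, and with symmetric scores and 50-70% zeros the usual standard error was right or slightly large. Nor should a 29% shortfall be taken as typical: at 20% in pain it needs a skewness of about 6. Right skew in every predictor is itself a guess, and quality of life need not be skewed that way.

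It is also fair to say that interval coverage describes an output the SAP does not plan, that the excess of false positives is modest, and that real factors as strong as those assumed would usually be detected under either method: in 95-99% of runs at 20% in pain with the usual errors and 84-97% with HC3.

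The deepest objection is that robust errors leave the larger problems alone. A straight line remains a poor description of a mostly-zero score, and P-values from a reduced model carry selection that no standard error corrects.

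All of this stands as a limit on the size and scope of the point. It does not remove the gap: the SAP cannot know the zero share or skew in advance, and it relies on an assumption that fails in plausible cases when a method that does not need that assumption is available.

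**Conclusion.** The point holds in conditional form. The SAP takes P-values for intensity from a constant-variance model without a safeguard, and the usual standard error of a real risk factor may be too small when zeros are very common (about 90%) or questionnaire scores are right-skewed.

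- **Symmetric scores:** little or no shortfall with at least 20% of children in pain; about 8% at 10% in pain, and 5-17% across the effect sizes tried with five predictors.
- **Mild to moderate skew (up to about 1.75):** about 9-15% at 20% in pain and 20-30% at 10%.
- **Extreme skew:** about 30-40%.

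The harm is mainly overstated precision for factors that are real. It would be wrong to infer that the analysis would produce findings from nothing, since rejection stays near 5% when no predictor matters.

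Prevalence, skew, effect sizes, predictor correlation, a 0-10 scale, two-sided testing and full follow-up are all assumptions. So is reading chronic pain as the 3- to 12-month visits. The change is worth making because it is cheap and holds under either variance pattern, not because a large error has been shown.

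**What to change.** State in the SAP that P-values for B in the intensity model, and 95% intervals if they are reported, come from HC3 heteroscedasticity-consistent standard errors or from a bootstrap that resamples children. Because the SAP fixes SPSS 25, it should also name the procedure that will produce them.

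The cost is one sentence and a software option. Where ordinary least squares was adequate (symmetric scores, 20-40% in pain), the mean HC3 standard error was within 4% of the usual one. Power falls where the usual errors were overconfident, generally slightly. The largest drop was with log-normal scores, 90% zeros and an odds ratio of 1.5, where detection went from 64% to 33%. In that setting the usual intervals covered only 79%, so part of the apparent power was not real; HC3 covered about 91%.

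The SAP should say that this corrects the standard errors only. Whether a linear mean suits a mostly-zero score, and how the reduced final model is selected, need their own statements.

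### The regression uses pain location as a linear outcome, names no outcome visit and omits pre-surgery pain, so a score that only marks existing pain can be reported as an independent risk factor

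*SAP*

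**What the plan says.** The SAP has two association analyses. In the first, "the Pearson Correlation Coefficient will be used" to relate the risk factors of children and parents to chronic postsurgical pain. The second is a multiple linear regression in which "the intensity and location of pain will be included as criterion variables". On the other side of that model stand five constructs: "catastrophizing, anxiety, fear of pain, fear of movement and quality of life will be considered as predictor variables". Coefficients and P-values "will be calculated for each predictor variable of the reduced final model", after which "it will be possible to determine the variables that most directly influence the regression model". Neither paragraph names a visit for the outcome or the predictors, and pre-surgery pain appears in neither.

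The protocol (Study design) has questionnaires completed at admission and pain assessed within 5 days of surgery. Then, "At 10 days, 3 months, 6 months and 12 months after the intervention", families are telephoned and "they will be asked to reply again to the evaluation of all the variables". The Sample section admits children from all surgical specialties. Its two exclusion criteria concern Spanish and verbal communication, not existing pain. The sample size of 260 comes from a rule of 20 children per predictor, set out for a prediction model.

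**The concern.** There are three gaps, of different kinds.

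- **Location.** Linear regression needs a numeric outcome. The SAP gives no numeric coding for location, so B, beta and adjusted R² for it have no meaning as written.
- **Outcome visit.** Pain is available at five post-surgery times. The word chronic points to a late one, but none is fixed, so the visit could be chosen after the results are seen.
- **Pre-surgery pain.** A child who already hurts may score higher on fear, anxiety or catastrophizing before surgery and may also hurt later. Without pre-surgery pain in the model, the score takes the credit for that continuity.

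The third gap matters most if results are read as factors that lead to new pain. The SAP's title is about developing chronic pain, and the protocol's Ethical Aspects section offers the study "in order to understand the mechanisms of chronic pain in the pediatric population".

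**Working it through.** **The plan's own figure.** 20 × 13 predictors = 260, which reproduces. I use n = 260 and P < 0.05, taken as two-sided.

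**Assumed inputs (the documents give no correlations).** Pre-surgery pain correlates a = 0.3–0.4 with each score and b = 0.3–0.5 with later pain. Scores correlate r = 0.3–0.6 with each other. No score has any effect of its own. The number of scores k is 5 (the SAP's constructs), or 9 if the four parent scores in the protocol's Sample section also enter (5 + 4).

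**Pearson step.** The correlation of a score with later pain is a × b. By Fisher's z, the standardised signal is atanh(ab) × √(260 − 3).
- ab = 0.3 × 0.3 = 0.09: signal 1.45, significant in 30% of studies.
- ab = 0.4 × 0.5 = 0.20: signal 3.25, significant in 90%.

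**Regression without pre-surgery pain.** For equally correlated scores:
- coefficient β = ab / (1 + (k − 1)r)
- VIF = (1 + (k − 2)r) / [(1 − r)(1 + (k − 1)r)]
- R² = k(ab)² / (1 + (k − 1)r)
- SE = √[(1 − R²) × VIF / (n − k − 1)]

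| k | a / b / r | β | VIF | R² | SE | β/SE | significant, per score |
|---|---|---|---|---|---|---|---|
| 5 | 0.3 / 0.3 / 0.6 | 0.0265 | 2.06 | 0.012 | 0.0895 | 0.30 | 6% |
| 5 | 0.4 / 0.5 / 0.3 | 0.0909 | 1.23 | 0.091 | 0.0665 | 1.37 | 28% |
| 9 | 0.3 / 0.3 / 0.6 | 0.0155 | 2.24 | 0.013 | 0.0941 | 0.16 | about 5% |
| 9 | 0.4 / 0.5 / 0.3 | 0.0588 | 1.30 | 0.106 | 0.0683 | 0.86 | 14% |

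Simulation agrees with these values and supplies the chance that at least one score is significant:

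| Scores | Without pre-surgery pain: per score | At least one | With it: per score | At least one |
|---|---|---|---|---|
| 5 | 6–28% | about 25–87% | 5% | 20–23% |
| 9 | about 5.5–14% | 39–79% | 5% | 35–37% |

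**What is left after adjustment.** For independent tests, 1 − 0.95⁵ = 23% and 1 − 0.95⁹ = 37%. The residual 20–37% is therefore multiplicity, a separate matter.

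**Prediction aim, five scores, same assumptions.** R² is 0.01–0.09 from the scores alone. With pre-surgery pain added it is b² = 0.09–0.25.

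**Open outcome visit.** If intensity were tested at 3, 6 and 12 months, a null predictor would be significant at least once in 1 − 0.95³ = 14% of studies were the visits independent, and in fewer when they are correlated.

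**The case against.** **Predictor timing is not really open.** A reader might infer that the SAP intends to relate scores and pain from the same follow-up visit. The documents do not support that. The design is prospective, there is a pre-surgery session, post-surgery pain is called the dependent variable, and the title concerns developing pain. Same-visit pairing is not forbidden, but nobody proposes it. Stating the timing is a clarification only.

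**The aim may be prediction.** The sample-size text speaks of a prediction model and the SAP of degree of association. The SAP's closing sentence is about influence on the regression model, not on pain. Under that aim a score that marks pre-surgery pain is legitimate. This stands: the false-signal reading applies only to claims of an independent factor. For prediction, the complaint is the milder one that a useful predictor is absent.

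**The calculation assumes its mechanism.** Every score is given no effect, and pre-surgery pain carries the whole association. At the weak corner the five-score gap is small, 27% against 22%. This also stands: the figures show what can happen, not this study's error rate. A reduced final model could add to the problem, but the SAP gives no reduction rule, so I put no figure on that.

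**Adjustment can remove a real effect.** If fear or catastrophizing itself raises pre-surgery pain, holding pain fixed hides part of its contribution. This is a good reason to show both models.

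**Location could be scored numerically**, for example as a count of sites. The SAP does not say so.

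**Conclusion.** The point holds in three parts of unequal weight. Linear regression on location is wrong as written and needs no assumption to show it. The missing outcome visit is a plain gap. The missing pre-surgery pain term is a cheap and worthwhile improvement. It is necessary only before a score is called an independent risk factor.

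The direction of the last part follows from any positive correlation of pre-surgery pain with both the scores and later pain. Its size rests wholly on the assumed ranges and runs from slight to large.

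A reader might go further and infer that the age groups must be set aside, or that sex and specialty must enter the model. Neither follows from these gaps.

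**What to change.** 1. Do not analyse location by linear regression. Treat it as categorical, for example pain at the operated site, yes or no, by logistic regression, with the number of terms limited by the number of events.
2. Name in advance the outcome visit for chronic pain, chosen by the investigators, and state that predictors are the pre-surgery values.
3. Report the intensity regression with and without pre-surgery pain intensity. Keep that term in the adjusted model when the model is reduced, and claim an independent factor only from the adjusted model.
4. Confirm that pre-surgery pain is recorded. The Study design section implies this, since the post-surgery questionnaires follow the pre-surgery session, but does not state it. If it is not recorded, add one item.

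**Cost.** This is SAP wording if pre-surgery pain is already recorded. If it is not, children already enrolled without the item cannot be adjusted.
- *Intensity model:* one more term. Under the plan's own rule, 5 scores plus pain is 6 × 20 = 120 children, and 9 scores plus pain is 10 × 20 = 200. Both are within 260, leaving room for 54% and 23% loss.
- *Location model:* it will be small. If 10–30% of 260 have pain at the operated site (assumed), there are 26–78 events, and 20 per term allows 1–3 terms.
- *Limits of adjustment:* it is imperfect if pain is measured with error. At an assumed reliability of 0.8, five null scores are still significant in 5–9% of studies each. Multiplicity across scores is untouched.
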